4.6.1 Nivolumab Dose Delay Criteria

Nivolumab administration should be delayed for the following:

- Grade ≥ 2 non-skin, drug-related adverse events with the following exceptions:
 - Grade 2 drug-related fatigue or laboratory abnormalities do not require a treatment delay
- Any Grade 3 skin, drug-related AE
- Any Grade 3 drug-related laboratory abnormalities with the following exceptions for lymphopenia, leukopenia, AST, ALT, or total bilirubin
 - Grade 3 lymphopenia or leukopenia does not require dose delay
 - If a patient has a baseline AST, ALT, or total bilirubin that is within normal limits, delay dosing for drug-related Grade ≥ 2 toxicity
 - If a patient has baseline AST, ALT, or total bilirubin within the Grade 1 toxicity range, delay dosing for drug-related Grade ≥ 3 toxicity
- Any adverse event, laboratory abnormalities, or undercurrent illness which in the judgment of the investigator, warrants delaying the dose of study medication.

4.6.1.1 Management Algorithms for Immuno-Oncology Agents

Immuno-oncology (I-O) agents are associated with adverse events that can differ in severity and duration from adverse events caused by other therapeutic classes. Nivolumab is considered an immuno-oncology agent in this protocol. Early recognition and management of adverse events associated with immuno-oncology agents may mitigate severe toxicity. Management algorithms can be found in the Investigator's Brochure and have been developed to assist investigators in assessing and managing the following groups of adverse events:

- Pulmonary toxicity
- Gastrointestinal toxicity (diarrhea or colitis)
- Endocrinopathies
- Hepatotoxicity (including asymptomatic LFT elevations)
- Renal toxicity
- Skin toxicity
- Neurological toxicity

For patients expected to require 4 weeks of corticosteroids or other immunosuppressants to manage the adverse event, consider recommendations provided in the Investigator's Brochure.

Tumor assessments for all patients should continue as per protocol even if dosing is interrupted.

4.6.2 Nivolumab Modifications

Nivolumab dose reductions and escalations are not permitted.

4.6.3 Criteria to Resume Treatment with Nivolumab

Patients may resume treatment with nivolumab when the drug-related AEs resolve to Grade ≤ 1 or baseline value with the following exceptions:

- Patients may resume treatment in the presence of Grade 2 fatigue
- Patients who have not experienced a Grade 3 drug-related skin AE may resume treatment in the presence of Grade 2 skin toxicity
- Patients with baseline AST/ALT or total bilirubin in the Grade 1 toxicity range who require dose delays for reasons other than a 2-grade shift in AST/ALT or total bilirubin may resume treatment in the presence of Grade 2 AST or ALT OR total bilirubin.
- Drug-related pulmonary toxicity, diarrhea, or colitis must have resolved to baseline before treatment is resumed
- Drug-related endocrinopathies adequately controlled with only physiologic hormone replacement may resume treatment
- If treatment is delayed > 6 weeks, the patient may be permanently discontinued from study therapy, except as specified in [Section 3.5](#).

4.6.4 Discontinuation Criteria for Nivolumab

BMS-936558 (nivolumab) treatment should be permanently discontinued for the following reasons:

- Any Grade 2 drug-related uveitis or eye pain or blurred vision that does not respond to topical therapy and does not improve to Grade 1 severity within the re-treatment period OR requires systemic treatment
- Any Grade 3 non-skin, drug-related adverse event lasting > 7 days, with the following exceptions for laboratory abnormalities, drug-related uveitis, pneumonitis, bronchospasm, hypersensitivity reactions, and infusion reactions:
 - Grade 3 drug-related uveitis, pneumonitis, bronchospasm, hypersensitivity reaction, or infusion reaction of any duration requires discontinuation
 - Grade 3 drug-related laboratory abnormalities do not require treatment discontinuation except:
 - ◆ Grade 3 drug-related thrombocytopenia > 7 days or associated with bleeding requires discontinuation
 - ◆ Any drug-related liver function test (LFT) abnormality that meets the following criteria require discontinuation:
 - AST or ALT $> 5-10x$ ULN for > 2 weeks
 - AST or ALT $> 10x$ ULN
 - Total bilirubin $> 5x$ ULN
 - Concurrent AST or ALT $> 3x$ ULN and total bilirubin $> 2x$ ULN

- Any Grade 4 drug-related adverse event or laboratory abnormality, except for the following events which do not require discontinuation:
 - Grade 4 neutropenia \leq 7 days
 - Grade 4 lymphopenia or leukopenia
 - Isolated Grade 4 electrolyte imbalances/abnormalities that are not associated with clinical sequelae and are corrected with supplementation/appropriate management within 72 hours of their onset
- Any dosing interruption lasting $>$ 6 weeks with the following exceptions:
 - Dosing interruptions to allow for prolonged steroid tapers to manage drug-related adverse events are allowed. Prior to re-initiating treatment in a patient with a dosing interruption lasting $>$ 6 weeks, the BMS Medical Monitor must be consulted. Tumor assessments should continue as per protocol even if dosing is interrupted.
 - Dosing interruptions $>$ 6 weeks that occur for non-drug-related reasons may be allowed if approved by the BMS Medical Monitor. Prior to re-initiating treatment in a patient with a dosing interruption lasting $>$ 6 weeks, the BMS Medical Monitor must be consulted. Tumor assessments should continue as per protocol even if dosing is interrupted.
- Any adverse event, laboratory abnormality, or intercurrent illness which, in the judgment of the Investigator, presents a substantial clinical risk to the patient with continued nivolumab dosing

4.6.5 Treatment Beyond Disease Progression

As described in [Section 1.1.2](#), accumulating evidence indicated a minority of patients treated with immunotherapy may derive clinical benefit despite initial evidence of progressive disease.³⁷

Patients treated with nivolumab will be permitted to continue treatment beyond initial Investigator-assessed progressive disease as long as they meet the following criteria:

- Investigator-assessed clinical benefit and do not have rapid disease progression
- Tolerance of study drug
- Stable performance status
- Treatment beyond progression will not delay an imminent intervention to prevent serious complications of disease progression (eg, CNS metastases)
- Patient provides written informed consent prior to receiving additional nivolumab treatment using an ICF describing any reasonably foreseeable risk or discomforts or other alternative treatment options
- The assessment of clinical benefit should be balanced by clinical judgment as to whether the patient is clinically deteriorating and unlikely to receive any benefit from continued treatment with nivolumab

If the investigator feels that the nivolumab patient continues to achieve clinical benefit by continued treatment, the patient should remain on the trial and continue to receive monitoring according to the Time and Events Schedule in [Table 5.1-2](#).

Global deterioration of health status requiring discontinuation of treatment without objective evidence of disease progression at the time should be reported as symptomatic deterioration. Every effort should be made to document objective progression (ie, radiographic confirmation) even after discontinuation of treatment.

The assessment of clinical benefit should take into account whether the patient is clinically deteriorating and unlikely to receive further benefit from continued treatment. All decisions to continue treatment beyond initial progression must be discussed in the study records.

4.6.6 Treatment of Nivolumab Related Infusion Reactions

Since nivolumab contains only human immunoglobulin protein sequences, it is unlikely to be immunogenic and induce infusion or hypersensitivity reactions. However, if such a reaction were to occur, it might manifest with fever, chills, rigors, headache, rash, pruritus, arthralgias, hypo- or hypertension, bronchospasm, or other symptoms. All Grade 3 or 4 infusion reactions should be reported within 24 hours to the BMS Medical Monitor and reported as an SAE if criteria are met. Infusion reactions should be graded according to NCI CTCAE (version 4.0) guidelines.

Treatment recommendations are provided below and may be modified based on local treatment standards and guidelines as appropriate:

For Grade 1 symptoms (mild reaction, infusion interruption not indicated, intervention not indicated):

Remain at bedside and monitor patient until recovery from symptoms. The following prophylactic premedications are recommended for future infusions: diphenhydramine 50 mg (or equivalent) and/or paracetamol 325 to 1000 mg (acetaminophen) at least 30 minutes before additional nivolumab administrations.

For Grade 2 symptoms (moderate reaction requires therapy or infusion interruption but responds promptly to symptomatic treatment [eg, antihistamines, non-steroidal anti-inflammatory drugs, narcotics, corticosteroids, bronchodilators, IV fluids], prophylactic medications indicated for ≤24 hours):

Stop the nivolumab infusion, begin an IV infusion of normal saline, and treat the patient with diphenhydramine 50 mg IV (or equivalent) and/or paracetamol 325 to 1000 mg (acetaminophen); remain at bedside and monitor patient until resolution of symptoms. Corticosteroid or bronchodilator therapy may also be administered as appropriate. If the infusion is interrupted, then restart the infusion at 50% of the original infusion rate when symptoms resolve; if no further complications ensue after 30 minutes, the rate may be increased to 100% of the original infusion rate. Monitor patient closely. If symptoms recur then no further nivolumab will be administered at that visit. Administer diphenhydramine 50 mg IV and remain at bedside and monitor the patient until resolution of symptoms. The amount of study drug infused must be recorded on the electronic case report form (eCRF). The following prophylactic medications are recommended for future infusions: diphenhydramine 50 mg (or equivalent) and/or paracetamol 325 to 1000 mg (acetaminophen) should be administered at least 30 minutes before additional nivolumab

administration. If necessary, corticosteroids (recommended dose: up to 25 mg of IV hydrocortisone or equivalence) may be used.

Grade 3 or 4 symptoms (severe reaction, Grade 3 prolonged [ie not rapidly responsive to symptomatic medication and/or brief interruption or infusion]; recurrence of symptoms following initial improvement; hospitalization indicated for other clinical sequelae [eg, renal impairment, pulmonary infiltrates]). Grade 4: (life-threatening, pressor or ventilatory support indicated):

Immediately discontinue infusion of nivolumab. Begin an IV infusion of normal saline and treat the patient as follows: recommend bronchodilators, epinephrine 0.2 to 1 mg of 1:1,000 solution for subcutaneous administration or 0.1 to 0.25 mg of 1:10,000 solution injected slowly for IV administration, and/or diphenhydramine 50 mg IV with methylprednisolone 100 mg IV (or equivalent) as needed. Nivolumab will be permanently discontinued. Investigators should follow their institutional guidelines for the treatment of anaphylaxis. Remain at bedside and monitor patients until recovery from symptoms. In the case of late-occurring hypersensitivity symptoms (eg, appearance of a localized or generalized pruritus within 1 week after treatment), symptomatic treatment may be given (eg, oral antihistamine or corticosteroids).

4.7 Blinding/Unblinding

Not applicable.

4.8 Treatment Compliance

Treatment compliance will be monitored by drug accountability as well as the patient's medical record and eCRF.

4.9 Destruction of Study Drug

For this study, study drugs (those supplied by BMS or sourced by the investigator) such as partially used study drug containers, vials and syringes may be destroyed on site.

Any unused study drugs can only be destroyed after being inspected and reconciled by the responsible Study Monitor unless study drug containers must be immediately destroyed as required for safety, or to meet local regulations (eg, cytotoxics or biologics).

On-site destruction is allowed provided the following minimal standards are met:

- On-site disposal practices must not expose humans to risks from the drug.
- On-site disposal practices and procedures are in agreement with applicable laws and regulations, including any special requirements for controlled or hazardous substances.
- Written procedures for on-site disposal are available and followed. The procedures must be filed with the site's SOPs and a copy provided to BMS upon request.
- Records are maintained that allow for traceability of each container, including the date disposed of, quantity disposed, and identification of the person disposing the containers. The method of disposal, ie, incinerator, licensed sanitary landfill, or licensed waste disposal vendor must be documented.
- Accountability and disposal records are complete, up-to-date, and available for the Monitor to review throughout the clinical trial period.

If conditions for destruction cannot be met the responsible Study Monitor will make arrangements for return of study drug.

It is the investigator's responsibility to arrange for disposal of all empty containers, provided that procedures for proper disposal have been established according to applicable federal, state, local, and institutional guidelines and procedures, and provided that appropriate records of disposal are kept.

4.10 Return of Study Drug

If study drug will not be destroyed upon completion or termination of the study, all unused and/or partially used study drug that was supplied by BMS must be returned to BMS. The return of study drug will be arranged by the responsible Study Monitor.

It is the investigator's responsibility to arrange for disposal of all empty containers, provided that procedures for proper disposal have been established according to applicable federal, state, local, and institutional guidelines and procedures, and provided that appropriate records of disposal are kept.

Arrangements for the return of study drug will be made by the responsible Study Monitor.

5 STUDY ASSESSMENTS AND PROCEDURES

5.1 Flow Chart/Time and Events Schedule

Table 5.1-1: Screening Procedural Outline (CA209172)

Procedure	Screening Visit ^a	Visit 1	Notes
Eligibility Assessments			
Informed Consent	X		
Inclusion/Exclusion Criteria	X		Assessed prior to first dose
Medical History	X		Documentation of mutation status (BRAF, NRAS, cKIT) if known.
Safety Assessments			
HIV testing (Germany only)	X		To be performed within 28 days of the first dose.
Physical Examination	X	X	Included height, weight, ECOG Performance Status. Focused physical exam performed at screening, if clinically indicated.
ECOG Performance Status	X	X	Cohort : PS 0-1 Cohort 2: PS 2
Vital Signs and Oxygen Saturation	X	X	Temperature, BP, HR, RR, O2 saturation by pulse oxymetry at rest (also monitor amount of supplement oxygen if applicable). Obtain vital signs at screening visit and within 72 hours of first dose.
Serious Adverse Events Assessment	X	X	
Adverse Events Assessment	X	X	
Assessment of Signs and Symptoms	X		After obtaining Informed Consent, assess all signs and symptoms within 14 days of first dose, prior to study treatment initiation
████████████████████	█	█	████████████████████
Laboratory Tests	X		Serum chemistry tests performed locally within 14 days prior to first dose (unless otherwise specified): CBC with differential, serum chemistry (BUN or serum urea level, serum creatinine, sodium, calcium, phosphate, chloride, and glucose), AST, ALT, total bilirubin,

Table 5.1-1: Screening Procedural Outline (CA209172)

Procedure	Screening Visit ^a	Visit 1	Notes
Pregnancy Tests	X	X ^b	alkaline phosphatase, albumin, LDH, TSH, free T3, freeT4, and lipase. Within 28 days prior to first dose, hepatitis B surface antigen (HBsAg) and hepatitis C antibody (HCV Ab). Performed within 24 hours prior to first dose for WOCBP only (serum or urine as required by the standard of care at the site). See Section 3.3.3 for the definition of Women of Childbearing Potential.
Additional Assessments			
EORTC QLQ-C30		X	Patient to complete
EQ-5D-3L		X	Patient to complete
Efficacy Assessments			
Screening/Baseline Tumor Assessments	-----see notes-----		Chest, abdomen, pelvis, brain, and other known sites of disease within 6 weeks prior to first dose of study therapy. Patients must have evaluable disease by CT or MRI per RECIST 1.1 criteria (radiographic tumor assessment performed within 6 weeks prior to first dose of study) or clinically apparent disease that the investigator can follow for response.

ALT = Alanine aminotransferase; AST = Aspartate aminotransferase; BP = blood pressure; BUN = blood urea nitrogen; CBC = complete blood count; HBsAg = hepatitis B surface antigen; HCV Ab = hepatitis C antibody; HR = heart rate; LDH = lactate dehydrogenase; O2 = oxygen; PS = Performance Status; RR = respiratory rate; TSH, thyroid stimulating hormone; WOCBP = women of child bearing potential

^a Within 6 weeks before start of nivolumab

^b Within 24 hours prior to the start of nivolumab (Day 1). An extension up to 72 hours prior to the start of nivolumab is permissible in situations where results cannot be obtained within the standard 24 hour window

Table 5.1-2: CA209172 On-Treatment Assessments

Procedure	Each Cycle (every 2 weeks) (±2 days)	Every 2 Cycles (every 4 weeks) (±2 days)	Every 3 Cycles (every 6 weeks) (±2 days)	Notes
Safety Assessments				
Physical Measurements (including PS)	X			Collect weight and ECOG PS within 72 hours prior to dosing. Focused physical exams should be performed as clinically indicated.
Vital Signs and Oxygen Saturation	X			Within 72 hours prior to dosing, tests include temperature, BP, HR, RR, O2 saturation by pulse oxymetry at rest (also monitor amount of supplemental oxygen if applicable) prior to dosing and at any time a patient has any new or worsening respiratory symptoms. Assessed using NCI CTCAE v 4.0.
Serious Adverse Event Assessments	X			For patients with known immune-related, Grades 3-4 adverse events during treatment with an anti-CLTA-4 antibody, weekly telephone calls or in-person visits are recommended.
Adverse Event Assessment	X			Assessed using NCI CTCAE V 4.0. For patients with known immune-related, Grades 3-4 adverse events during treatment with an anti-CTLA-4 antibody, weekly telephone calls or in-person visits are recommended.
				
Laboratory Tests	X		X (TFTs only)	CBCs with differential, ^a Serum chemistry tests, ^b liver function tests ^c and lipase should be checked every cycle, and the results should be obtained prior to dosing. TFTs ^d should be checked every 3 cycles (every 6 weeks) starting with Cycle 1. May be completed more frequently if required by local standards. Laboratory tests should be completed 72 hours prior to dosing, and the results must be available prior to dosing. See footnote b regarding availability of lipase results prior to dosing.
Pregnancy Test		X		Completed every 2 cycles, starting with Cycle 1. May be completed more frequently if required by local standards

Table 5.1-2: CA209172 On-Treatment Assessments

Procedure	Each Cycle (every 2 weeks) (±2 days)	Every 2 Cycles (every 4 weeks) (±2 days)	Every 3 Cycles (every 6 weeks) (±2 days)	Notes
Efficacy Assessments				
Tumor Scans	---	---see notes---		Mandatory initial tumor assessment is to be completed at Week 12 (±5 days). If known or new CNS metastases are detected during screening, a brain scan is required at the mandatory tumor assessment at Week 12 (±5 days). Further tumor assessments are recommended to be completed as required by local standards of care or at the investigator's discretion and are recommended every 8 weeks. The assessment of clinical benefit should be balanced by clinical judgment as to whether the patient is clinical deteriorating and unlikely to receive any benefit from continued treatment with nivolumab.
Survival	X			
Outcomes Assessments				
EQ-5D-3L		X		Every 2 cycles (4 weeks) for 4 months starting with Cycle 1, then every 4 cycles (8 weeks) after first administration of nivolumab prior to any study procedures and treatments
EORTC QLQ-C30		X		Every 2 cycles (4 weeks) for 4 months starting with Cycle 1, then every 4 cycles (8 weeks) after first administration of nivolumab prior to any study procedures and treatments
Clinical Drug Supplies				
Administration of Study Drug	X			

BP = blood pressure; CBC = complete blood count; HR = heart rate; LDH = lactate dehydrogenase; LFT = liver function test; NCI CTCAE = National Cancer Institute Common Terminology Criteria for AEs; O2 = oxygen; PS = Performance Status; RR = respiratory rate; TFT, thyroid function test.

^a CBCs with differential includes white blood cell count, lymphocyte count, absolute neutrophil count, hemoglobin, hematocrit, and platelet count. Results to be obtained prior to dosing on infusion days

- b Serum chemistry tests include blood urea nitrogen [BUN] or serum urea level, serum creatinine, sodium, calcium, chloride, lipase, and glucose. Amylase should be performed in addition to lipase in cases where lipase results are not available prior to dosing.
- c Liver function tests include AST, ALT, total bilirubin, alkaline phosphatase, albumin.
- d Thyroid function testing including TSH (free T3 and free T4 if abnormal results for TSH).

Table 5.1-3: Off-Treatment Follow-Up Assessments:CA209172

Procedure	Every 4 Weeks	FU-X01 (30 days ±7 days)	FU-X02 (70-84 days after FU- X01 ±7 days)	Follow-Up After X01 and X02. Every 3 months. (±7 days)	Notes
Safety Assessments					
Physical Examinations		X	X		Collect weight and ECOG PS. Focused physical examination may be performed if clinically indicated.
Vital Signs and Oxygen Saturation		X	X		Temperature, BP, HR, RR, O2 saturation by pulse oximetry at rest (also monitor amount of supplemental oxygen if applicable) prior to dosing and at any time a patient has any new or worsening respiratory symptoms.
Adverse Events Assessments		X	X		Beyond 100 days from the last dose of study therapy, patients followed for ongoing drug-related adverse events until resolved, symptoms return to baseline or are deemed irreversible, lost to follow-up, or withdrawal of study consent.
		■	■		
Laboratory Tests		X	X		Serum chemistry tests and TFTs should be checked at FU1 and FU2.
Pregnancy Test	X	X	X		Pregnancy testing may be performed at home if an in-office visit is otherwise not required.
Efficacy Assessments					
Tumor Scans				-----see notes-----	Tumor progression scans are recommended to be completed as required by local standards of care or at the investigator's discretion.

Table 5.1-3: Off-Treatment Follow-Up Assessments:CA209172

Procedure	Every 4 Weeks	FU-X01 (30 days ±7 days)	FU-X02 (70-84 days after FU- X01 ±7 days)	Follow-Up After X01 and X02. Every 3 months. (±7 days)	Notes
Survival Follow-up		X	X	X ^a	
Outcomes Assessments					
EQ-5D-3L		X	X	X ^a	The EQ-5D-3L can be completed by mail, e-mail, or telephone call (using the telephone version) when a clinical visit is not otherwise required. When a clinical visit is required, the questionnaire should be completed at the clinic.

BP = blood pressure; CBC = complete blood count; HR = heart rate; LDH = lactate dehydrogenase; LFT = liver function test; NCI CTCAE = National Cancer Institute Common Terminology Criteria for AEs; O2 = oxygen; PS = Performance Status; RR = respiratory rate; TFT, thyroid function test.

^a For subjects who have discontinued treatment before the end of the 2-year treatment period. Per Amendment 08, follow up begins when the decision to discontinue a patient from study therapy is made (no further treatment with nivolumab) and continues from first dose of study therapy up to 2 years or until death, withdrawal of study consent, or lost-to-follow-up.

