3 INVESTIGATIONAL PLAN

3.1 Study Design and Duration

The study will include patients with histologically-confirmed stage III (unresectable) or stage IV advanced melanoma who have documented progression after treatment containing an anti-CTLA-4 monoclonal antibody. Patients will be treated with 3 mg/kg of nivolumab IV every 2 weeks for a maximum of 24 months. Patients will undergo screening evaluations to determine eligibility within 6 weeks prior to the first dose following the signing of an informed consent. Each 14-day dosing period will constitute a cycle.

The Scientific Steering Committee will evaluate the clinical risk/benefit ratio closely following a defined Safety Management Plan.

Patients will undergo screening evaluations to determine eligibility as indicated in [Table 5.1-1](#) prior to first dose following signed informed consent. Patient's demographic data will be collected: date of birth, gender, disease stage, date of diagnosis, previous treatments, comorbidities,

performance status, lactate dehydrogenase (LDH) level, type of melanoma (mucosal, uveal), and mutation status if known (BRAF, NRAS, cKIT).

Safety, including adverse event monitoring and physical examination, should be monitored continually, and safety assessments are discussed in [Table 5.1-2](#).

Mandatory initial tumor assessments are to be done at Week 12 (± 5 days). Further tumor assessments should be performed according to institutional standard of care and are recommended every 8 weeks until:

- disease progression
- a concurrent malignancy requires treatment
- the patient is lost to follow up
- the patient withdraws study consent
- completed 24 months of treatment

Patients will not be permitted to continue their treatment beyond initial Investigator-assessed progressive disease unless they meet the following criteria:

- Investigator-assessed clinical benefit
- Patient is tolerating study drug

The investigator should use his or her clinical judgment to assess clinical benefit by considering whether the patient is clinical deteriorating and unlikely to receive any benefit from continued treatment with nivolumab.

Per Amendment 08, follow up begins when the decision to discontinue a patient from study therapy is made (no further treatment with nivolumab) and continues from first dose of study therapy up to 2 years or until death, withdrawal of study consent, or lost-to-follow-up.

The cohorts are described in [Table 3.1-1](#).

Table 3.1-1: Patient Cohorts

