5.3 Safety Assessments

Only data for the procedures and assessments specified in this protocol should be submitted to BMS on a case report form. Additional procedures and assessments may be performed as part of standard of care; however, data for these assessments should remain in the patient's medical record and should not be provided to BMS unless specifically requested. NCI CTCAE version 4.0 will be the criteria used to assess severity of AEs.

During the 100 days after the last dose of study treatment, patients will have 2 additional follow-up visits as described in [Table 5.1-3](#).

The following assessments should be monitored starting on Cycle 1 Day 1 and will continue as per the schedule in the Time and Events Tables at the specified frequency until discontinuation from study therapy:

- Adverse events continuously throughout the study
- Physical examination and physical measurements including weight and ECOG PS
- Complete blood count with differential, including white blood cells, lymphocyte count, absolute neutrophil count, hemoglobin, hematocrit, and platelet count. Results to be obtained prior to dosing on infusion days.
- Serum chemistry tests (blood urea nitrogen or serum urea level, serum creatinine, sodium, calcium, phosphate, chloride, glucose, lipase, and LDH). Results to be obtained prior to dosing on infusion days. Amylase should be performed in addition to lipase in cases where lipase results are not available prior to dosing.
- Liver function tests including AST, ALT, total bilirubin, alkaline phosphatase, and albumin. Results to be obtained prior to dosing on infusion days.

- Thyroid function testing including thyroid stimulating hormone (free T3 and free T4 if abnormal results for TSH)

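### Liver function tests are not named at the two off-treatment safety visits, so new asymptomatic hepatic select AEs may be missed or found late

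*Protocol*

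**What the plan says.** Table 5.1-3 sets the off-treatment assessments. Its laboratory row covers FU-X01 (30 ± 7 days) and FU-X02 (70 to 84 days later, ± 7), and the note reads "Serum chemistry tests and TFTs should be checked at FU1 and FU2". The table gives no definition of either panel.

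On treatment, the note in Table 5.1-2 lists serum chemistry and then adds that "liver function tests ^c and lipase should be checked every cycle". Protocol 5.3 gives liver function tests (LFTs) their own bullet, apart from serum chemistry. It runs its whole list "at the specified frequency until discontinuation from study therapy" and refers the two post-treatment visits to Table 5.1-3. Under Protocol 3.1, "follow up begins when the decision to discontinue a patient from study therapy is made".

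Other text bears on hepatic events off treatment:

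- Protocol 4.6.1.1 (cited by 8.3.1) and SAP 4.1 count symptom-free liver test elevations within the hepatic select AE category.
- Protocol 6.2.1 collects nonserious AEs for at least 100 days after the last dose.
- Protocol 8.4.2.1 presents the primary endpoint both on and off treatment. 8.4.2.2 separates on-treatment from post-treatment AEs.
- SAP Appendix 1 follows time to onset of select AEs to 30 or 100 days after the last dose, depending on the analysis.
- AE assessment and physical examination take place at both visits. Beyond 100 days, "patients followed for ongoing drug-related adverse events until resolved".

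**The concern.** A symptom-free rise in transaminases or bilirubin is found only by a blood test. Such rises belong to a category of the primary endpoint, and the protocol undertakes to report that endpoint off treatment. If neither follow-up visit carries an LFT, a new Grade 3 or higher elevation after stopping is seen only when a site happens to test. The same holds for potential drug-induced liver injury, which Protocol 6.6 defines by transaminases and bilirubin.

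The visits do test for neighbouring categories: TFTs cover the thyroid, and creatinine and urea cover the kidney. No reason for leaving out the liver is visible.

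Nor is the period free of exposure. Protocol 3.3.1 takes five half-lives as 125 days, so one is 125/5 = 25 days. On simple half-life decay, 0.5^(30/25) = 44% of the drug remains at day 30 and 0.5^(100/25) = 6% at day 100.

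Any missed event lowers the observed incidence, which is the direction that favours the hypothesis of low frequency.

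**Working it through.** **Step 1. What does serum chemistry mean?**

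- Table 5.1-2, footnote b: "Serum chemistry tests include blood urea nitrogen [BUN] or serum urea level, serum creatinine, sodium, calcium, chloride, lipase, and glucose". None of these seven items is a liver test.
- Table 5.1-2, footnote c: "Liver function tests include AST, ALT, total bilirubin, alkaline phosphatase, albumin". This is a separate panel.
- Protocol 5.3 and the synopsis list the two panels as separate items.
- Table 5.1-1 (screening) points the other way. Its note opens "Serum chemistry tests performed locally within 14 days prior to first dose (unless otherwise specified" and goes on to list AST, ALT, bilirubin, alkaline phosphatase and albumin.

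Two features weaken the broad reading. Within the screening note, serum chemistry appears again with its own bracketed list, apart from AST and ALT. The opening words also stand over the thyroid tests, so if Table 5.1-3 used the term that broadly it would not need to name TFTs. The narrow reading is therefore better, but not certain.

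**Step 2. Does other visible text schedule an off-treatment LFT?** None was found. LFT appears among the abbreviations under Table 5.1-3, but that list matches the one under Table 5.1-2 and also contains CBC, which the follow-up cell does not name. One row of Table 5.1-3 is blacked out. It is unlikely to hold LFTs, because in Tables 5.1-1 and 5.1-2 they sit in the visible laboratory row.

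**Step 3. When do the visits fall?** Assume FU-X01 is counted from the last dose.

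- FU-X01: 30 ± 7 = day 23 to 37.
- FU-X02, nominal: 30 + 70 = 100 to 30 + 84 = 114.
- FU-X02, with both windows: (30 − 7) + (70 − 7) = 86 to (30 + 7) + (84 + 7) = 128.

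FU-X01 lies inside the 100 days but may fall on either side of the SAP's 30-day cut. FU-X02 nominally lies at or after day 100 and falls earlier only if the windows are used.

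Table 5.1-3 does not state the anchor. If counting starts at a decision made L days after the last dose, add L to each figure. With L = 42 as an assumed example, FU-X01 is day 65 to 79 and FU-X02 is nominally day 142 to 156.

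**Step 4. How large could the effect be?** The plan states no figure for this, and the documents give neither an off-treatment hepatic rate nor the share that local testing would find. What follows is illustration only. Take N = 800 treated (Protocol 8), an assumed true risk q of new asymptomatic Grade 3 or higher hepatic events off treatment of 0.25% to 2%, and an assumed share s detected without scheduled LFTs of 0% to 100%. Expected events are N × q, and observed events are N × q × s.

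| q | expected | observed, s from 0% to 100% |
|---|---|---|
| 0.25% | 2 | 0 to 2 |
| 1% | 8 | 0 to 8 |
| 2% | 16 | 0 to 16 |

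At q = 1% and s = 50%, 4 of 8 are seen. The estimate is 4/800 = 0.5% (exact 95% CI 0.14% to 1.28%) instead of 8/800 = 1.0% (0.43% to 1.96%). As a check of the method, 3/640 gives 0.10% to 1.36%, which agrees with the 0.1% to 1.4% in Protocol 8.1 and SAP 5.

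**The case against.** The strongest reply is that the cell is merely unclear. Separate naming does not prove separate panels: the Table 5.1-2 note names lipase separately although footnote b already includes it. Definitions also drift, since Protocol 5.3 puts phosphate and LDH in serum chemistry and footnote b does not. Footnotes b and c belong to Table 5.1-2, not 5.1-3. This stands as a reason for caution, and it is why the point covers both readings. It does not remove the problem, because a cell that sites can read in two ways also gives uneven testing.

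A second reply is that safeguards exist. Protocol 6.3 makes clinically significant laboratory results reportable, 6.6 does so for potential liver injury, and 6.7 extends to assessments the protocol does not require. This stands for elevations that someone finds. It does not help a patient with no local test, and follow-up to resolution covers events already under way, not new ones.

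A third reply is that the follow-up panel may be deliberately reduced, since CBC is also missing. That is possible, but symptom-free liver elevations are expressly part of the primary endpoint and the blood is drawn anyway.

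Four stronger inferences are tempting and should not be drawn:

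- That Protocol 5.3 proves LFTs stop at discontinuation. The same phrase governs AEs, physical examination, chemistry and TFTs, all of which continue in Table 5.1-3.
- That about seven tests are lost (100/14 = 7.1). Those on-treatment tests are pre-dose checks, and no dose follows discontinuation.
- That the full 100 days after the last dose go untested. LFTs may still be done after the last dose while a patient remains on study therapy, for example during a dose delay.
- That the primary result is materially biased. An elevation counts only if it is recorded as an AE, graded 3 or higher and judged related. SAP 7.6.1.1 shows no on/off-treatment split, and the SAP's time-to-resolution clusters use on-treatment events only.

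**Conclusion.** The point holds, with limited reach. On the better reading, neither of the two safety follow-up visits carries an LFT. On the broader reading, the instruction is ambiguous. In both cases new asymptomatic Grade 3 or higher hepatic select AEs may be missed or detected late in patients without a local LFT, during a period for which the protocol promises AE collection and off-treatment presentation of the primary endpoint.

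The size cannot be derived and is probably small. As rough context, Protocol 1.4.3 reports that fewer than 5% of nivolumab patients in CA209037 had Grade 3–4 select AEs of any category. New symptom-free hepatic events off treatment would be a fraction of such a figure. The analyses are descriptive, so no test or decision rule changes.

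The conclusion assumes that the blacked-out row holds no liver tests, and the day counts assume that FU-X01 is counted from the last dose. The Core Safety SAP is not among the documents; it could change how off-treatment events are tabulated, but an analysis plan would not add a test to a visit. The change should be made, but nothing else in the plan depends on it.

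**What to change.** Reword the laboratory cell of Table 5.1-3 so that it requires three panels at both FU1 and FU2: serum chemistry, liver function tests (AST, ALT, total bilirubin, alkaline phosphatase, albumin) and TFTs. This settles either reading.

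If FU-X01 is counted from the last dose, the change reliably adds one LFT inside the 100-day window, at FU-X01, and one at about its end, at FU-X02. It should not be described as two tests within the window.

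For visits already completed without LFTs, add one sentence to the report: hepatic select AEs off treatment were not systematically ascertained and their incidence may be underestimated.

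The cost is one table cell, one sentence in the report if visits have passed, and a small laboratory charge. Blood is already drawn at both visits.
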